9.4.2 Primary Endpoint

The primary endpoint is the overall incidence of RSV LRTI hospitalization through the RSV season in healthy term and preterm infants in all 3 countries combined. The determination of RSV LRTI hospitalization is based on the criteria described in Section 8.1.2.2.

The efficacy of nirsevimab in preventing RSV LRTI hospitalization compared to no intervention will be estimated accounting for the follow-up time post-dosing/randomization up to the data cut-off date for the Primary Analysis as follows:

 $(1-(CN/NN)/(CC/NC)) \times 100\%$

where:

- CN and CC are the numbers of RSV LRTI hospitalization through the RSV season in the nirsevimab and the control (ie, no intervention) groups, respectively.
- NN and NC are the total person-time contributed by participants randomized in the nirsevimab and the control groups, respectively.

The 95% CI for the efficacy will be calculated by an exact method assuming a binomial distribution of the number of RSV LRTI hospitalizations in the nirsevimab group conditional on the total number in both groups accounting for the follow-up time post-dosing/randomization.

The superior efficacy of nirsevimab in preventing RSV LRTI hospitalization will be concluded if the lower bound of the efficacy is > 0%. The primary efficacy analysis of the primary endpoint will be performed on all randomized participants.

If a participant experiences multiple occurrences of the same primary endpoint, only the first episode will be considered. The following rules will be applied in the calculation of the total person-time for the follow-up time:

- The start date for the follow-up will be the date of randomization for participants who are randomized to no intervention and the date of dosing for participants who are randomized to nirsevimab.
- For the participants who do not have the primary endpoint at the time of the Primary Analysis, the end date for the efficacy follow-up will be the end of the RSV season, or the last available date with confirmation of no RSV LRTI hospitalization for the Primary Analysis whichever is earlier. The efficacy follow-up will be censored at the end date.
- For the participants who have the primary endpoint at the time of the Primary Analysis, the end date for the efficacy follow-up will be the date of hospital admission.

The above-described analysis on the primary endpoint will also be conducted on the PPAS.

A sensitivity analysis using a Poisson regression model with robust variance will be performed on all randomized participants (60). The model contains the term of treatment group, and age group at randomization (ie, age ≤ 3.0 months, age > 3.0 to ≤ 6.0 months, age > 6.0 months) and country as covariates, adjusting for the log of the follow-up time as an offset. The efficacy of nirsevimab in preventing RSV LRTI hospitalization, defined as 1 minus Relative Risk, and its corresponding 2-sided 95% CI will be estimated from the model. The same rule used in the analysis for the primary endpoint as described above for the calculation of total follow-up time will be applied to the calculation of the follow-up time.

A Kaplan-Meier curve for time to first RSV LRTI hospitalization will be generated based on the observed events. The algorithm for time-to-event calculation is the same as that for follow-up time as above. Treatment group differences in time to first RSV LRTI hospitalization will be compared using the log-rank test stratified by country and age group at randomization. In addition, hazard ratio and the corresponding 95% CI will be obtained from the Cox proportional hazard model with age group at randomization and country as the covariates. The corresponding efficacy estimate is defined as (1-harzard ratio) × 100%.

The subgroup analysis of the primary endpoint will be conducted on the following in all randomized participants using the exact method described above in the primary efficacy analysis:

- Age group at randomization: age \leq 3.0 months, age > 3.0 to \leq 6.0 months, age > 6.0 months
- Weight at randomization: weight $\leq 5 \text{ kg}$, weight $\geq 5 \text{ kg}$
- Gestational age: < 37 weeks, ≥ 37 weeks
- Gender: male, female
- Infants dosed in-season (dosed on or after the start date of RSV season) and before the start of the RSV season.

Note: please refer to Section 4.2 for a definition of the start and the end of RSV season

Additional analyses if deemed necessary will be detailed in the SAP.

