6.3 Measures to Minimize Bias: Randomization and Blinding

6.3.1 Randomization and Allocation Procedures

On the day of randomization, participants who meet all the inclusion criteria but none of the exclusion criteria with a signed informed consent from the parent(s) or other LAR will be

randomly assigned to Group 1 (nirsevimab) or Group 2 (no intervention) in a 1:1 ratio, stratified according to country and age at the time of randomization (ie, age \leq 3.0 months, age > 3.0 to \leq 6.0 months, and age > 6.0 months).

Site staff will connect to the IRT, enter the identification and security information, and confirm a minimal amount of data in response to IRT prompts. The IRT will then provide the subject randomization number and the group assignment and have the site staff confirm it. The full detailed procedures for group allocation are described in the IRT user guidelines. If the participant is not eligible to participate in the study, then the information will only be recorded on the participant recruitment log. If the parents or LARs of a participant have signed the consent but the participant is not randomized, the participant number and the reason of the screening failure will be recorded in the IRT database and then transferred in the clinical database.

Participant randomization numbers that are assigned by the IRT will consist of a 12-digit string (a 3-digit country identifier, a 4-digit study center identifier, and a 5-digit participant identifier). For example, Participant 250000100005 is the fifth participant enrolled in Center Number 1 in France (250 being the France country code). Participant numbers should not be reassigned for any reason.

The randomization codes will be kept securely in the IRT.

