 - for the participants who had no contact for safety events at all throughout the efficacy follow-up period, the end date for the efficacy follow-up will be date of randomization for participants who are randomized to no intervention, the date of treatment dosing for participants who are randomized to nirsevimab and treated, and the date of randomization for participants who are randomized to nirsevimab but not treated.

The total person-time for the follow-up time of each participant will be calculated as:

Person-months = (the end date - the start date + 1)/30.4375.

NN (days), the total person-time contributed by participants randomized in the nirsevimab, will be the sum of person-months for all the participants in the nirsevimab group. And NC (days), the total person-time contributed by participants randomized in the no intervention group, will be the sum of person-months for all the participants in the no intervention group.

The 2-sided 95% CI for the efficacy will be calculated by an exact method assuming a binomial distribution of the number of RSV LRTI hospitalizations in the nirsevimab group conditional on the total number in both groups (described by Breslow and Day⁷) accounting for the follow-up time post-dosing/randomization.

The superior efficacy of nirsevimab in preventing RSV LRTI hospitalization is concluded if the lower bound of 2-sided 95% CI of the efficacy is $> 0\%$. P-value will also be provided. The primary efficacy analysis of the primary endpoint will be performed with the All Randomized Set.

RSV season is the period of increased RSV infection. For the purpose of efficacy analyses, the start of the RSV season will be defined on a country-by-country basis and will be based on country-specific epidemiological surveillance and the cut-off date (28Feb2023, except for site parent contact and medical call center contact, for which the date of database lock for Primary Analysis will be used) will be used as end dates.

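### The confirmatory exact analyses pool across the randomization strata (country and age group), which leaves a small, avoidable bias if follow-up loss differs by arm and stratum

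*Protocol*

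**What the plan says.** Protocol 6.3.1 allocates infants "in a 1:1 ratio, stratified according to country and age at the time of randomization". Three countries and three age groups give nine strata. SAP 2.1 repeats this.

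For the primary endpoint, Protocol 9.4.2 defines efficacy as 1 − (CN/NN)/(CC/NC), where "NN and NC are the total person-time contributed by participants randomized in the nirsevimab and the control groups, respectively". The interval comes from "an exact method assuming a binomial distribution of the number of RSV LRTI hospitalizations in the nirsevimab group conditional on the total number". SAP 6.6.1 uses the same method, "conditional on the total number in both groups (described by Breslow and Day", and superiority "is concluded if the lower bound of 2-sided 95% CI of the efficacy is" above 0%. There is no stratum term in either document and no reason is given for leaving it out.

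Very severe RSV LRTI uses the same method (Protocol 9.4.3.1, SAP 6.6.4.1). So do the country tests (Protocol 9.4.3.2, SAP 6.6.4.2), which condition on country by construction but not on age group.

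The strata do appear elsewhere:
- a robust Poisson sensitivity model ("The model contains the term of treatment group, and age group at randomization", with country as a further covariate; SAP 6.6.2.1);
- a "log-rank test stratified by country and age group at randomization" and a Cox model with both factors (SAP 6.6.3.2);
- the corresponding Poisson, Cox and log-rank analyses of the key secondary endpoints (SAP 6.6.5 and 6.6.6);
- subgroup analyses by age (SAP 6.6.8).

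None of these decides success, and neither document says how to read an adjusted result that disagrees with the crude one.

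**The concern.** An analysis that follows the randomization strata is the natural counterpart of stratified allocation. Here there is also a specific reason to want it.

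Person-time is not fixed by design. Infants without an event are censored no later than the last date on which absence of hospitalization was confirmed. Under SAP 6.6.1, infants with no contact at all have an end date equal to their start date. Follow-up therefore depends on parents responding, and parents know the allocation. Protocol 6.3.2 accepts that equal attention to the two groups cannot be assured, and SAP 6.6.2.2 anticipates possible excess withdrawal among controls.

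If that loss is also uneven across strata with different RSV risk, the two arms' person-time ends up with different stratum mixes, and the crude ratio picks up that difference. Within-stratum comparison does not. At stake is a small shift in the headline efficacy and, in the least favourable cases, in the operating characteristics of the test.

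**Working it through.** **1. The plan's own figures (Protocol 9.2).** These reproduce under the unstratified exact conditional test. The nirsevimab share of events is 0.5 under no effect and 0.4/1.4 = 0.2857 at 60% efficacy.

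| Events | Two-sided alpha | Exact power |
|---|---|---|
| 73 | 1.66% | 88.4% |
| 74 | 1.66% | 91.4% |
| 60 | 5% | 89.2% |
| 61 | 5% | 92.2% |

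Expected events per country are 4810 × 1.1% × 1.4 = 74.07. The sizing therefore matches the pooled analysis as written.

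**2. Balanced person-time.** With 1:1 allocation in each stratum, the nirsevimab count in stratum s is about Binomial(d_s, 0.5) under no effect, so the sum is about Binomial(D, 0.5). The stratified exact test is then nearly the pooled one. Simulation over nine strata, 4000 trials per scenario, gave these rejection rates (pooled / stratified):

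| N, control rate | No effect | 60% efficacy |
|---|---|---|
| 28 860, 0.86% | 1.85% / 1.85% | 100% / 100% |
| 28 860, 0.4% | 2.25% / 2.25% | 97.1% / 97.1% |
| 8000 (assumed), 0.86% | 1.68% / 1.70% | 82.0% / 82.0% |

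The two tests disagreed in at most 0.13% of trials in any scenario. Stratifying costs no power and does not change the 74 or 61 events.

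**3. Unbalanced person-time: mild example.** The documents give no stratum shares, relative risks or dropout rates, so all of these are assumed. Age shares are 50/25/25% and relative risks 2:1:0.5, youngest to oldest. True rate ratio is 0.4, and only controls lose follow-up.

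- Nirsevimab mean rate: 0.4 × (0.5×2 + 0.25×1 + 0.25×0.5) = 0.4 × 1.375 = 0.55.
- Controls lose 10% of person-time in the youngest stratum: (0.45×2 + 0.25 + 0.125)/0.95 = 1.3421. Crude ratio 0.55/1.3421 = 0.4098, efficacy 59.0%.
- A 5% loss there: (0.475×2 + 0.25 + 0.125)/0.975 = 1.3590. Ratio 0.4047, efficacy 59.5%.
- A 10% loss in the oldest, lowest-risk stratum instead: (1 + 0.25 + 0.225×0.5)/0.975 = 1.3974. Ratio 0.3936, efficacy 60.6%.

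In each case the within-stratum ratio is 0.4, so a stratified estimate stays at 60%.

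**4. Steeper gradients.** Same shares; relative rates 3:1.5:1 or 5:2:1; control loss of 5 to 20% in the youngest or the oldest stratum. The extremes come from 5:2:1 with 20% loss. The nirsevimab rate is 0.4 × 3.25 = 1.3.

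- Loss in the youngest stratum: control rate (2.0 + 0.5 + 0.25)/0.90 = 3.0556. Ratio 0.4255, efficacy 57.5%.
- Loss in the oldest stratum: control rate (2.5 + 0.5 + 0.2)/0.95 = 3.3684. Ratio 0.3859, efficacy 61.4%.

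With no true effect, the same two cases give 1 − 3.25/3.0556 = −6.4% and 1 − 3.25/3.3684 = +3.5%.

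One-sided rejection under no effect was computed at 61 events and at 174 events, the latter from 14 430 × 0.86% × 1.4 = 173.7. Against a nominal 2.5%, the highest values are 3.15% and 3.23%, both with loss in the oldest stratum. With the same loss in the youngest stratum they fall to 0.7% and 0.8%.

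**The case against.** The strongest reply is that this concerns which analysis carries the primary label. Each confirmatory endpoint already has prespecified analyses that use the randomization factors. The SAP also meets differential dropout directly, with a tipping-point analysis (6.6.2.2, extended to both key secondary endpoints) and a covariate-adjusted comparison of time to discontinuation (6.6.7.5). The pooled exact test matches the sizing. Nine strata would be thin if the Primary Analysis ran at 61 events (61/9, about 7 per stratum), and the mild example with loss in the youngest stratum works against nirsevimab.

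Much of this stands. A reader might infer that the strata are ignored altogether, or enter only the Poisson model. The documents do not support either: stratified log-rank and Cox analyses are prespecified too. Nor do the country tests ignore country; only age is left out.

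Three parts do not settle the matter. The tipping-point analysis imputes events for missing infants without stratifying, so it does not replace a stratified estimate. The bias can run either way, so it is not reliably conservative. Sparse strata do not invalidate an exact conditional analysis; a stratum without events simply contributes nothing.

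Timing is a fair objection. The current SAP is version 6.0 of 14 January 2025, the primary cut-off was 28 February 2023, and SAP section 7 reports the re-run of the Primary Analysis in the past tense. Replacing the confirmatory test after results are known would be post hoc.

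**Conclusion.** The point holds as a minor one. The confirmatory exact analyses do not follow the randomization strata, no reason is given, and the omission leaves a small bias of either sign if follow-up loss differs by arm and varies by stratum. Its size is about 0.5 to 1 efficacy point in the mild example, and a reading between 57.5% and 61.4% for a true 60% under the steeper assumptions. If person-time is balanced within strata, the conclusions are essentially unchanged. All shares, risk gradients and losses are assumptions; the documents neither give them nor show that such loss occurred.

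Two stronger readings should be resisted. One is that the primary test is invalid or its error rate seriously inflated: even the most extreme case examined gives about 3.2% one-sided. The other is that stratifying would cure dropout bias. It corrects the mixing of strata only, and only if loss is non-informative within each stratum.

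**What to change.** At design stage, make the primary and very severe RSV LRTI analyses exact conditional rate-ratio analyses stratified by country × age group, and stratify the country tests by age group. Keep the crude exact interval as supportive. The adjusted Poisson model could serve instead, but it gives up exactness.

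If the primary results are already known, leave the crude test as confirmatory. Report the stratified exact estimate and interval beside it, labelled as added afterwards. Add a sentence justifying the unstratified choice and saying how a discordant adjusted result will be read.

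The cost is a few lines of SAP text and slightly more analysis work. Sample size and event targets stay as they are.

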9.4.3 Secondary Endpoints

9.4.3.1 Very severe RSV LRTI

If the efficacy of nirsevimab in preventing RSV LRTI hospitalization is demonstrated in the primary efficacy analysis, the very severe RSV LRTI through the RSV season will be compared between the nirsevimab and no intervention groups on all randomized participants using the same method for the primary efficacy analysis of the primary endpoint. The very severe RSV LRTI is a subset of RSV LRTI hospitalization with oxygen saturation < 90% (at any time during hospitalization) and oxygen supplementation. For participants with multiple very severe RSV LRTI episodes, only the first occurrence will be used in the analysis. If the lower bound of the 95% CI for the efficacy is > 0%, the superior efficacy of nirsevimab in preventing very severe RSV LRTI compared to the control group is demonstrated.

The above stated analysis on very severe RSV LRTI will be also conducted on the PPAS. The time to first very severe RSV LRTI will be analyzed using the Kaplan Meier curve and the Cox proportional hazard model, as described for the primary efficacy endpoint in Section 9.4.2, on all randomized participants.

Incidence of the very severe RSV LRTI will be summarized by the following subgroups:

- Age group at randomization: age \leq 3.0 months, age > 3.0 to \leq 6.0 months, age > 6.0 months
- Weight at randomization: weight $\leq 5 \text{ kg}$, weight $\geq 5 \text{ kg}$
- Gestational age: < 37 weeks, ≥ 37 weeks
- Gender: male, female
- Infants dosed in-season (dosed on or after the start date of the RSV season) and before the start of the RSV season.
- Country

Note: please refer to Section 4.2 for a definition of the start and the end of RSV season

Additional analyses if deemed necessary will be detailed in the SAP.

9.4.3.2 RSV LRTI Hospitalization in each country

If the efficacy of nirsevimab in preventing very severe RSV LRTI compared to the control is concluded, RSV LRTI hospitalization will be evaluated in each of the 3 countries. The same analysis as described above in Section 9.4.2 the primary efficacy analysis for the primary endpoint with Bonferroni-Holm procedure based on the adjusted CIs for the multiplicity adjustment will be used to calculate the efficacy on all randomized participants in each country. The superior efficacy

of nirsevimab in preventing RSV LRTI hospitalization will be concluded for the country if the lower bound of the efficacy is > 0%.

Additional analyses if deemed necessary will be detailed in the SAP.

9.4.3.3 Other secondary efficacy endpoints

Efficacy and its 95% CIs for nirsevimab in reducing the following efficacy endpoints as compared to the control will be calculated using the exact method as described in the primary efficacy analysis for the exploratory purpose:

- Overall hospitalization for all-cause LRTI in all 3 countries combined throughout the RSV season
- RSV LRTI hospitalization through 150 days post-dosing/randomization (overall and in each country)
- Very severe RSV LRTI in all 3 countries combined through 150 days postdosing/randomization
- Overall hospitalization for all-cause LRTI in all 3 countries combined through 150 days post-dosing/randomization
- RSV LRTI hospitalization through 180 days post-dosing/randomization (overall and in each country)
- Overall hospitalization for all-cause LRTI in all 3 countries combined through 180 days post-dosing/randomization
- Recurrent wheeze throughout the study period in UK reconsented participants

Analyses for the above efficacy endpoints through 150 days post-dosing/randomization and through 180 days post-dosing/randomization will be performed only at the First Year Analysis after all data are collected. Details of the analyses and additional analyses if deemed necessary will be described in the SAP.

Descriptive analyses of the incidence of RSV LRTI hospitalization and all-cause LRTI hospitalization and the incidence of recurrent wheeze with its 95% CIs for nirsevimab and the no intervention will be presented in UK reconsented participants.

9.4.4 Exploratory Endpoints

Efficacy and its 95% CIs for nirsevimab in reducing the following efficacy endpoints as compared to the control will be calculated using the exact method as described in the primary efficacy analysis for the exploratory purpose:

 Very severe RSV LRTI in all 3 countries combined through 180 days postdosing/randomization

Analyses for the above efficacy endpoints through 180 days post-dosing/randomization will be performed only at the Final Analysis after all data are collected. Details of the analyses and additional analyses if deemed necessary will be described in the SAP.

For other exploratory endpoints, tabular summaries will be presented by the 2 arms. Categorical data will be summarized by the number and percentage of participants in each category. Continuous variables will be summarized by descriptive statistics. Additional details of statistical analyses will be described in the SAP.

9.4.5 Safety Analysis

Safety endpoints will be analyzed based on the SafAS defined in Section 9.3. Safety of nirsevimab will be assessed by the occurrence of immediate AEs, non-serious AEs within 30 days post-dosing/randomization, and MAAEs, SAEs, and AESIs following 12 months post-dosing/randomization for all participants, related SAEs from D366 to D731 for UK reconsented participants. All AEs will be coded by MedDRA system organ class and preferred term. The type, incidence, and severity will be summarized by treatment group. Relationship to nirsevimab will also be summarized.

In addition, all AEs (including immediate AEs, non-serious AEs within 30 days post-dosing/randomization, and MAAEs, SAEs and AESIs) in neonates < 28 days of age at randomization will be summarized.

